Research Protocol

(Version No. 2.3 Version Date: 2024.08.02)

Project Name : Observation of the clinical effect of a new oropharyngeal airway in patients with obstructive sleep apnea hypopnea syndrome during painless gastroenteroscopy

Department: Anesthesia and perioperative Medicine

Main Investigator: [name]

Investigator Statement and Protocol signature page

As the principal investigator of this research project, Will be guided by the ethical principles of the Guidelines on the Issuance of Ethical Review of Life Sciences and Medical Research Involving Humans (2023), the Ethical Review of Biomedical Research Involving Humans (2016), the WMA Declaration of Helsinki (2013) and the CIOMS International Ethical Guidelines on Biomedical Research on Humans (2002) and the GCP, The study shall be conducted in accordance with the requirements of the protocol approved by the Ethics Committee under the guidance of the quality Management Practice for drug clinical research, in order to ensure the scientific study and protect the health and rights of the study participants.

signature: _____

Date: _____

Scheme summary

Scheme title	Observation of clinical effect of new oropharyngeal airway in patients with obstructive sleep apnea hypopnea syndrome during painless gastroenteroscopy
Version number/version date	Version Number 2.3 Version Date: 2024.08.02
Main Investigator	[name]
Nature of the study	Randomized, controlled clinical intervention study
Prospective	
Objective To investigate	the incidence of hypoxia in patients with obstructive sleep apnea hypopnea syndrome who underwent painless gastroenteroscopy using a new type of oropharyngeal airway.
Sample size	130
Subjects Obstructive	sleep apnea hypopnea syndrome patients undergoing painless gastroenteroscopy
Inclusion criteria	(1) Age 18-65 years old (2) evidence of polysleep monitoring for diagnosis of OSAHS (3) written informed consent of patient or family member (4) painless stomach + colonoscopy (5) ASA grade I-II
Exclusion criteria	(1) There is a clotting disorder or a tendency to nose and mouth bleeding, mucosal damage or space occupation, Patients who cannot perform oropharyngeal ventilation (2) upper respiratory tract infections such as mouth, nose or throat (3) fever (core body temperature $\geq 37.5^{\circ}\text{C}$) (4) diagnosed pregnancy or breastfeeding (5) allergy to sedatives such as propofol or devices such as tape (6) emergency surgery (7) multiple trauma (8) Breathing air before surgery $\text{pO}_2 < 95\%$ (9) History of drug and/or alcohol abuse (drinking more than three times standard alcoholic beverages per day, equivalent to approximately 10g of alcohol or equivalent to 50g of Chinese liquor) in the 2 years prior to initiation of the screening period (10) Patients with prior psychiatric and neurological conditions: Such as depression, severe central nervous depression, Parkinson's disease, basal ganglia disease, schizophrenia, epilepsy, Alzheimer's disease,

	
myasthenia gravis (11) are currently participating in other clinical trials
 
(13) Patients with a history of smoking should not participate in this trial

Research program	
Heart rate, pulse oxygen saturation (SpO₂), end-expiratory carbon dioxide, ECG monitoring, and noninvasive blood pressure (measured every 3 minutes) were routinely monitored before anesthesia induction. In this study, SAS was used to achieve simple randomization: 1. In the group using the new oropharyngeal airway (test group), oxygen was continuously supplied through a catheter connected to the endoscopic bites until the end of the gastroenteroscopy before induction of anesthesia. 2. In the conventional endoscopic bite group (control group), oxygen was continuously supplied through a conventional nasal catheter before induction of anesthesia and until the end of gastroenteroscopy. Before anesthesia induction, patients in the experimental group received 5-6L/min of oxygen for about 1min through the endoscopic bite connecting oxygen supply device, and patients in the control group inhaled 5-6L/min of oxygen for about 1min through the nasal catheter. Propofol 3mg/kg and sufentanil 7μg were used to induce anesthesia in both groups. Sufentanil was given at the beginning of pre-oxygen inhalation, and propofol was given 1min later. When participants achieved sufficient sedation (about BIS40), the new oropharyngeal airway group was placed into the oropharyngeal airway through the endoscopic bite and then began gastroscopy. The ordinary endoscopic bite group began to perform endoscopic operation after sufficient sedation was achieved. In both groups, 5mg/kg·h propofol was injected continuously to maintain anesthesia until the examination was completed. If participants showed frowning or slight body movement during diagnosis and treatment, 40 to 50mg of propofol was added intravenously. If HR < 50 times/intravenous injection of atropine 0.5mg; MAP < 60mmHg intravenous hydroxyamine 1mg; When SpO₂ < 92%, artificial airway intervention such as jaw support, assisted breathing or mask was given. After the examination is completed, the patient should not leave the examination room until the MOAA/S is 3-4 points. If the sedation/anaesthesia

	Discharge rating scale scores more than 9 points, patients can be accompanied by relatives and friends. The incidence of hypoxia ($75\% \leq \text{SpO}_2 < 90\%$, $\leq 60\text{s}$) and severe hypoxia ($\text{SpO}_2 < 75\%$ or $75\% \leq \text{SpO}_2 < 90\%$, $\geq 60\text{s}$) during anesthesia were recorded. The incidence of choking, reflux aspiration and laryngeal spasm were recorded. The time of intervention was half or disappearance of end-expiratory carbon dioxide and/or disappearance of thoracic fluctuation and/or $\text{SpO}_2 < 95\%$, that is, open airway manipulation was taken successively until $\text{SpO}_2 \geq 95\%$, and the last means of opening the airway was recorded. The means of opening the airway of the two groups were the same, including: 1) adjusting the oxygen flow; 2) Lift the lower jaw; 3) Mask ventilation (pull out the gastroscope if necessary); 4) Tracheal intubation or laryngeal mask for ventilator assisted ventilation.
Shedding/culling criteria	After postoperative recovery, patients were assessed for adverse reactions. The score of discharge scale after sedation/anesthesia was more than 9 points. Patients could be accompanied by relatives and friends to leave the hospital.
Shedding/culling criteria	Patients who were lost to follow-up, had adverse events, or voluntarily withdrew from the trial
Early exit criteria	Patients with severe airway spasm, obstruction of ventilation, inability to effectively improve airway, and need emergency tracheal intubation or cricothyroid puncture.
Primary outcome measure	Incidence of hypoxia ($75\% \leq \text{SpO}_2 < 90\%$, $\leq 60\text{s}$) during anesthesia and sedation.
Secondary outcome measure	1, severe hypoxia ($\text{SpO}_2 < 75\%$ or $75\% \leq \text{SpO}_2 < 90\%$, $\geq 60\text{s}$) 2, the incidence of airway intervention 3, intraoperative dose of additional drugs 4, endoscopist satisfaction 5, recorded adverse events: choking, laryngeal spasm and reflux aspiration incidence; Apnea or slow breathing episodes (defined as respiratory rate ≤ 6 beats/min); Bradycardia is defined as a heart rate ≤ 50 beats/min. Serious adverse events such as tracheal intubation, non-invasive ventilation, use of vasopressors, and hospitalization are required.

Safety index	1. Primary outcome measures: incidence of hypoxia 2. Secondary outcome measures: (1) incidence of airway intervention (2) monitoring of vital signs at different time points 3. Adverse events: (1) Intraoperative laryngeal spasm, reflux aspiration, hypotension, hypoxia saturation, respiratory depression, bradycardia/tachycardia etc. (2) postoperative: Pharyngeal pain, oropharyngeal hemorrhage, wake score, etc. 4. Satisfaction: patient, endoscopist
Statistical analysis method	SPSS22.0 statistical software package was used for statistical analysis, and the measurement data were expressed in the form of mean \pm standard deviation ($x \pm S$). Independent sample t test was used for statistical analysis of the data with normal distribution or transformed data conforming to normal distribution. For non-normal data, wilcoxon rank sum test was used to compare inter-group analyses. Counting data were represented by frequency (%), and Chi-square test was used for statistical analysis. $P < 0.05$ was considered to be statistically significant.
Research progress plan	1. From July 2024 to August 2024, improve the study design, formulate relevant CRF tables, pass ethics and register online; 2. From August 2024 to May 2025, complete case enrollment; 3. From June 2025 to September 2024, summarize data, make statistical analysis, and write the paper
Form of publication of research results	The results of the study will be published in the form of a paper, and 1-2 articles included in SCI will be published.

一、 Objective

1. Primary outcome measures

To investigate the incidence of novel oropharyngeal airway hypoxia ($75\% \leq \text{SpO}_2 < 90\%$, $\leq 60\text{s}$) during anesthesia in patients with obstructive sleep apnea hypopnea syndrome undergoing painless gastroenteroscopy.

2. Secondary outcome measure

(1) Incidence of severe hypoxia ($\text{SpO}_2 < 75\%$ or $75\% \leq \text{SpO}_2 < 90\%$, $\geq 60\text{s}$)

(2) The incidence of airway intervention required

(3) the dosage of additional drugs during the operation was recorded

(4) the satisfaction of endoscopists was recorded

(5) Adverse events were recorded: the incidence of choking, laryngeal spasm and reflux aspiration were observed; Apnea or slow breathing episodes (defined as respiratory rate ≤ 6 beats/min); Bradycardia is defined as a heart rate ≤ 50 beats/min. Serious adverse events such as tracheal intubation, non-invasive ventilation, use of vasopressors, and hospitalization are required.

3. Exploratory index

To observe whether the use of a new oropharyngeal airway during anesthesia can effectively reduce the incidence of adverse events other than hypoxia in patients with obstructive sleep apnea hypopnea syndrome undergoing painless gastroenteroscopy, and its safety and efficacy.

Research background

In recent years, gastroscopy has been applied more and more in clinical practice. It is a new endoscopic examination technology that finds all possible small lesions in the upper digestive tract (esophagus, stomach, duodenum) of patients through white light gastroscopy, and performs chemical staining, electron staining, optical/electronic amplification, targeted biopsy, etc., for suspicious lesions with indistinguishable properties, so as to clarify the nature of the lesions. This technology can improve the diagnostic rate of early gastric cancer and is a major breakthrough in the early diagnosis of gastric cancer ^[1]. Compared with ordinary gastroscopy, gastroscopy takes a longer time (it may take longer if suspicious lesions are found) and intraoperative airway management is more difficult.

Obstructive sleep apnea hypopnea syndrome (obstructive sleep apnea hypoapnea syndrome OSAS) is a kind of to sleep appear periodically in the process of syndrome characterized by partial or complete obstruction of upper respiratory tract. Patients with obstruction during the attack, faced with percutaneous arterial blood oxygen saturation (percutaneous arterial oxygen saturation, SpO₂) to reduce the risk of can also trigger hypercapnia and cardiovascular dysfunction. The global incidence of OSAS is 4.0% in males and 2.0% in females ^[2]. Sedative drugs inhibit the response of OSAS patients to external stimuli and may cause pharyngeal muscle collapse, leading to an increased risk of respiratory adverse events during painless gastroscopy in this population ^[3]. In fact, OSAS has been identified as an independent risk factor for endoscopic hypoxia ^[4]. Currently, there is no special oropharyngeal ventilation device used during gastroenteroscopy. Recently, a new type of oropharyngeal ventilation channel has been developed and applied in clinic. Compared with the conventional nasal catheter, the new oropharyngeal airway nasal mask can better fit the patient's face, ensure the air tightness inside the nose mask and maximize the oxygen supply efficiency. The carbon dioxide outlet connected to the oropharyngeal airway body can not only collect the patient's exhaled gas, but also reduce the backflow of carbon dioxide gas. It can also access carbon dioxide detection equipment to monitor the patient's PCO₂ at the end of breath in real time ^[5-6]. In order to evaluate whether the new oropharyngeal airway can reduce the incidence of

hypoxia during painless gastroenteroscopy in general patients, the study was designed to investigate the safety and efficacy of the new oropharyngeal airway. The new oropharyngeal airway is composed of nasal plug, biting mouth, oropharyngeal passage, oxygen supply tube, lanyard and optional accessories carbon dioxide gas catheter and carbon dioxide collection tube. It is used to prevent airway obstruction due to retrolingual fall in patients undergoing endoscopic surgery/examination, and to establish an oropharyngeal airway for study participants while providing nasal oxygen.

【reference】

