1.3 Exclusion/removal criteria

- 1) The patient voluntarily withdrew the informed consent
- 2) the operation was cancelled

2. Grouping of study participants:

This study planned to implement simple randomization with SAS: Group 1 was the group using the new oropharyngeal airway (experimental group);The other group was the control group (control group).

3. Blinded/unblinded patients This study was an open trial, and no blinded method was used.

4. Remedial and supportive treatment (necessary treatment measures for the occurrence of SAE related to the study)

(1) Continue to inject propofol with a range of 5ml to achieve the appropriate depth of anesthesia again if coughing, limb struggle and other conditions occur during the procedure;

(2) If severe airway spasm, obstruction of ventilation occur during the operation, and the airway cannot be effectively improved, measures such as mask pressure oxygen, emergency tracheal intubation or cricothyroid puncture should be taken. In the event of intraoperative emergencies and accidents, patients should be treated primarily, and patients should be put in the first place in accordance with clinical routine rescue and treatment of study participants.

5. Study Participant Early withdrawal/Trial termination criteria: Unconditional termination of the trial at any time when a study participant proposes to withdraw from the trial, while still guaranteeing patient safety throughout the process.

Research program

1. Study Participant Management

1) Study participant recruitment methods: The staff participating in this clinical trial was responsible for recruitment under the control of the principal investigator. 130 patients with obstructive sleep apnea hypopnea syndrome (diagnosed as OSAHS by polysomnography monitoring) who met the enrollment criteria and intended to undergo painless gastrocolonoscopy in our hospital were initially screened, and the recruitment materials were distributed to the study participants and their families.

2) Informed consent process: When enlisting study participants, inform study participants and their families of the detailed contents of the study, possible risks and benefits (see informed consent for details) in accordance with the content and requirements of informed consent, obtain consent from study participants and their families, and sign informed consent before anesthesia induction.

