- 3) Check the admission criteria: Participants were selected strictly according to the admission and exclusion criteria, and should be checked before entering the operating room and before anesthesia induction.
2. Safety evaluation procedure: Study participants with oropharyngeal tumor, inflammation, infection, ulcer and other bleeding risk withdrew from the test, and ventilation should not be used.
3. Termination and withdrawal procedures: Study participants with severe airway spasm, obstruction of ventilation, or failure to effectively improve airway, requiring emergency tracheal intubation or cricothyroid puncture, should immediately take life-saving measures and automatically withdraw from the study.
4. This study was conducted in collaboration with the Department of Anesthesia and Perioperative Medicine, the Department of Digestive endoscopy, and the Sleep Disorder Diagnosis and Treatment Center of Neurology. In the stages of study participant recruitment and trial conduct, tasks are allocated according to the professional background and skills of each team member to ensure that everyone's responsibilities are clear and they can work together.

The beginning and end of the experiment

Start: Trial is expected to begin after ethical review in July-August 2024.

End: Clinical trial phase is expected to end in May-June 2025.

Clinical criteria for early termination of trials

Criteria for termination: The study should be terminated if participants had severe airway spasm, obstruction of ventilation, or inability to effectively improve airway, or if emergency tracheal intubation or cricothyroid puncture were required. Or withdrawal of informed consent by study participants requires termination of the trial.

Data security and monitoring Programme

1. Overview of data Management methods Original records refer to all kinds of data, text, charts, pictures and other original materials directly recorded or statistically formed by means of experiment, observation, investigation or data analysis in the process of clinical and scientific research. The original record is the direct record of the original data obtained in the process of scientific experiment, which can be used as the important basic data for in-depth research in different periods. The original test records should be able to reflect the most real and original conditions in the test, and

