4. Communication with Ethics Committee and superior drug regulatory authorities Conduct clinical trials in accordance with the content of ethical approval, and timely communicate with ethics committee and superior drug regulatory authorities when there are problems encountered in the course of the trial or when the trial plan needs to be modified. Consent is required to change the test protocol. Communicate when there is a problem.

5. The entry and management of the internal data analysis plan shall be the responsibility of the designated data manager. In order to ensure the accuracy of the data, two data managers should independently make two copies of the input and proofread. For problems in the case report, the data manager will produce an answer sheet and send an inquiry to the investigator through the Clinical Ombudsman, who should answer and return as soon as possible. The data manager will modify, confirm and enter the data according to the researcher's answers.

Compliance with ethical principles and related regulations

This trial will be conducted in accordance with the research protocol, the Guidelines for the Ethical Review of Life Sciences and Medical Research Involving Humans (2023), the Guidelines for the Ethical Review of Biomedical Research Involving Humans (2016), the WMA Declaration of Helsinki (2013), and the CIOMS International Ethical Guidelines for Biomedical Research on Humans (2002). Health institutions conducting investigator-initiated Clinical Research Management Measures (Trial) and Ethical Principles of GCP research implement all applicable laws and regulations of the country. Conduct the study only after obtaining written approval from the Ethics Committee (IRB/IEC) on the protocol, informed consent, and study participant recruitment materials/processes. The proposed amendments also require IRB/IEC approval.

Statistical analysis plan

1. Analysis Set

(1) Full analysis Set (FAS) : All randomized study participants who were evaluated for efficacy at least once were deleted from the analysis set for data that were not evaluated for efficacy at least once.

(2) Meeting protocol set (PP) : Study participants in FAS who met the inclusion criteria and did not meet the exclusion criteria, completed the CRF form as planned, and did not use drugs that might affect the efficacy evaluation during the trial. Safety Dataset (SS) : Study participants who received at least one treatment after randomization.

2. Statistical Analysis

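### The summary's shedding/culling row removes patients who had adverse events, which in this protocol include the primary outcome, and conflicts with section 1.3 and the analysis sets

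*Protocol*

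**What the plan says.** The Shedding/culling criteria row of the Scheme summary names "Patients who were lost to follow-up, had adverse events, or voluntarily withdrew from the trial". The next rows make severe airway emergencies a ground for early exit and define the primary outcome as the incidence of hypoxia.

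Three places make desaturation an adverse event:
- The Safety index row lists, under adverse events, "Intraoperative laryngeal spasm, reflux aspiration, hypotension, hypoxia saturation, respiratory depression, bradycardia/tachycardia etc".
- Objective, item 3 (Exploratory index), asks whether the device "can effectively reduce the incidence of adverse events other than hypoxia", which counts hypoxia as one of them.
- Data security and monitoring Programme, item 2, defines an adverse event as any adverse symptom or abnormal sign after the intervention, whatever its cause.

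On withdrawal, Research program, item 3, says that participants "requiring emergency tracheal intubation or cricothyroid puncture, should immediately take life-saving measures and automatically withdraw from the study".

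Other sections differ. Research Methods 1.3 has two removal grounds: "The patient voluntarily withdrew the informed consent", and cancellation of the operation. The Statistical analysis plan section defines the full analysis set (FAS) as "All randomized study participants who were evaluated for efficacy at least once" and the safety set as "Study participants who received at least one treatment after randomization". Research Methods, item 3, states: "This study was an open trial, and no blinded method was used".

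**The concern.** A removal rule that depends on adverse events is, in this trial, a rule that depends on the primary outcome. Choking, laryngeal spasm, aspiration, slow breathing and bradycardia are likewise both adverse events and secondary outcomes. Patients withdrawn for emergency intubation or cricothyroid puncture are among those whose airway intervention and serious adverse events the trial sets out to count, yet the protocol does not say that their events are kept.

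If the rule is applied equally in both arms, event rates, the risk difference and power all fall. If it is applied unequally, the comparison is biased, and the direction depends on which arm loses more events. Because the trial is open-label, whoever decides whether a patient is shed or counted knows the arm.

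**Working it through.** **Inputs.** From Research content, item 2 (Sample size calculation): hypoxia rates 0.2 (test) and 0.5 (control), two-sided alpha 0.05, power 0.9, 52 evaluable per group, 20% shedding, 65 per group, 130 in total.

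**The plan's own figure.** Two proportions, pooled variance under the null, no continuity correction, with mean rate 0.35:

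n = [1.960·√(2·0.35·0.65) + 1.282·√(0.5·0.5 + 0.2·0.8)]² / 0.30² = (1.322 + 0.821)² / 0.09 = 51.01, rounded up to 52.

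Then 52 / (1 − 0.20) = 65. Both stated figures reproduce. In this calculation the protocol uses shedding to mean patients lost from the evaluable sample.

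**Literal culling of every hypoxic patient.**
- Test: 0.2 × 65 = 13 removed, 52 left.
- Control: 0.5 × 65 = 32.5 removed, 32.5 left.
- Overall: 45.5 / 130 = 35%, against 20% planned.
- The hypoxia rate among those left is 0 in both arms, so the primary comparison has no events.

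**Partial culling (illustration; the culled shares are assumptions).** If a share c of hypoxic patients is removed from an arm with true rate p:
- patients left = 65(1 − pc)
- observed rate = p(1 − c) / (1 − pc)
- observed odds = (1 − c) · p / (1 − p)

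Power and false-positive rate come from full enumeration of the two-sided uncorrected chi-square test at 0.05, with patient numbers rounded.

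| Scenario | n test / control | Observed rates | Probability of rejection |
|---|---|---|---|
| No culling | 65 / 65 | 0.20 vs 0.50 | 0.959 |
| Both arms, c = 0.25 | 62 / 57 | 0.158 vs 0.429 | 0.910 |
| Both arms, c = 0.50 | 58 / 49 | 0.111 vs 0.333 | 0.806 |
| Both arms, c = 0.80 | 55 / 39 | 0.048 vs 0.167 | 0.491 |
| Control only, c = 0.50 | 65 / 49 | 0.200 vs 0.333 | 0.369 |
| No true effect (0.35 in both), test only, c = 0.25 | 59 / 65 | 0.288 vs 0.35 | 0.115 |
| No true effect (0.35 in both), test only, c = 0.50 | 54 / 65 | 0.212 vs 0.35 | 0.383 |

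The first five rows are power; the last two are false-positive rates, to be compared with 0.05. A simulation that lets the numbers remaining vary (400,000 runs) gives 0.915, 0.814, 0.494, 0.368, 0.116 and 0.382 for the six culling rows in order.

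**Effect measures under equal culling.** The factor (1 − c) cancels from the odds ratio, which stays at 0.25. At c = 0.50 the risk difference falls from 0.30 to 0.333 − 0.111 = 0.222, and the risk ratio moves from 0.40 to 0.111 / 0.333 = 0.33.

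Removing patients for other adverse events would add to these losses. The protocol gives no rates for those events.

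**The case against.** The strongest defence is that the literal reading cannot be intended. The adverse-event clause stands between loss to follow-up and voluntary withdrawal, so it probably means leaving the trial because of an adverse event. The row names no analysis set. Elsewhere the protocol requires hypoxia and all adverse events to be recorded, analyses hypoxia by frequency, and defines analysis sets with no such exclusion. Planning rates of 0.2 and 0.5 with 20% shedding could not coexist with culling every hypoxic patient. The partial-culling shares have no basis in the text.

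Much of this is fair. Full literal culling is unlikely to be carried out, and the partial scenarios only show what the wording would permit. But the milder reading is not what the row says. Severe airway events already have their own early-exit row, so this clause covers something broader. Even on the milder reading, section 1.3 lists no such ground, so the passages still disagree. The missing-data rule in the Statistical analysis plan section, which allows cases with missing values to be deleted, leaves a further way for an incomplete early exit to drop out.

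The early-exit point is narrower: these are emergencies, the text does not say that recorded data are discarded, and it bears mainly on secondary and safety outcomes. Naming a primary analysis set could be left to a separate analysis plan, and the finding does not depend on it.

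**Conclusion.** The concern holds. As written, the summary row makes removal depend on the primary outcome and contradicts section 1.3, the FAS and the safety set. It is not established that these patients will be lost, because the protocol does not say which rule governs.

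The 35% loss with no primary events left follows from the protocol's own rates if the row is applied literally to hypoxia. The other power and false-positive figures rest on assumed culled shares and, for the false-positive case, an assumed common rate of 0.35. They show that discretionary use of the clause could weaken the trial or bias it in either direction. This should be fixed; the sample size of 65 per arm needs no change on this account.

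**What to change.** Delete the adverse-event clause from the Shedding/culling criteria row. Reconcile that row, the early-exit row and Research program, item 3, with section 1.3 and the analysis-set definitions. Then state that:
- an adverse event or early exit may end study procedures but does not end inclusion in the analysis;
- data recorded up to exit are kept;
- hypoxia or severe hypoxia (where the SpO₂ criteria were met), airway intervention and serious adverse events are counted for these patients.

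It would also help to name the FAS as the primary analysis set, here or in the separate analysis plan.

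The cost is wording plus the ethics committee approval that the protocol requires for amendments. The clinical exit and rescue rules are untouched, and the events are already recorded during the procedure.
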